### **E. Design and methods (including experimental design, technical details and laboratory methodology):**

#### **Design & Methods**

In this prospective unblinded pilot study we will enroll eligible patients until 20 parent/child dyads complete the study. It is expected many of the consented patients will not meet the eligibility criteria of CFS score > 6 (moderate severity of PSH). Those children will be considered Screen Failures and their parents/LAR told they are ineligible to continue in the study. Children admitted to the PICU at CW aged 2-17 years with ASBI and symptoms of PSH with a CFS score > 6 (moderate severity of PSH) will be eligible for inclusion. Exclusion criteria include age < 2 years (small ears thus less surface area to apply the leads), ear deformity or severe dermatitis of ear lobes, intractable seizures, heart block, patients with other implantable devices (cardiac pacemaker, vagal nerve stimulator, etc.) or known pregnancy.

#### **Study treatment**

Patients with ASBI are routinely co-managed by the ICU Neurology team who have extensive experience diagnosing and treating PSH. Potentially eligible patients will be identified by the ICU Neurologists (Co-I). Once enrolled, the PENFS device will be placed over the external ear and will remain continuously active for 120 hours. CFS scores will be calculated before and after initiation of PENFS as per study protocol.

#### **Medication detail during study treatment:**

No additional maintenance medications (propranolol, bromocriptine, dantrolene, gabapentin, baclofen) will be allowed to be initiated for the first 12 hours after initiation of PENFS. Patients could continue to receive rescue medications (morphine, benzodiazepines such as lorazepam, midazolam, diazepam, clonidine) during this period for break through symptoms or remain on maintenance medications that were already in

## Protocol Summary/Submission Application

place that would normally be used to treat PSH. Additional maintenance medications could be instituted beyond the initial 12-hour period if PSH symptoms are not adequately controlled. Initiation of maintenance medications before placement of PENFS will not be a contraindication to enrollment, but once enrolled, no new maintenance medications would be allowed for the initial 12 hours after device placement.

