
Aim 1: Demonstrate the feasibility of use of PENFS to treat PSH, and tolerability of the device. Hypothesis: The PENFS device will be well tolerated, defined as < 10% early termination from the study. We will recruit 20 patients with ASBI and PSH who will receive PENFS therapy.
 
Aim 2a: Evaluate the feasibility of capturing pediatric PSH symptoms using the CFS scoring tool. Hypothesis: It is feasible to monitor the severity of PSH using a CFS scoring tool (Table 1a,1b). The scoring tool will be adapted for the appropriate age range of the patient (Table 2). We aim for at least 80% scoring (<math>\geq 8/10</math> scheduled scoring per protocol while the device is worn).
 
Aim 2b: Evaluate the effectiveness of the PENFS device in reducing PSH symptoms using change in CFS score. Hypothesis: A decrease in CFS severity score with use of PENFS will be associated with a lower number and/or doses of maintenance and rescue medications for control of PSH symptoms.
 
Aim 3a: Evaluate the change in autonomic balance with use of PENFS device Hypothesis: Heart Rate Variability (HRV) and pupillometry parameters that correspond to sympathetic and parasympathetic activity will be different after PENFS device placement compared to before, reflecting an increase in parasympathetic tone. All patients will be on routine continuous EKG monitoring in the PICU during the study period of interest. Similarly, pupillometry is routinely performed in patients with ASBI in the PICU.
 
Aim 3b: Evaluate feasibility of measuring PENFS effectiveness in treating PSH by a decrease in medication use. Hypothesis: It would be feasible to use the maintenance and rescue medication dosing and frequency as a marker of severity of PSH. PENFS device use will result in lesser number and/or doses of maintenance and rescue medications for control of PSH symptoms. We will compare the pilot sample to a historical cohort to allow power analysis and sample size calculation for a future larger efficacy trial, recognizing that this pilot study is not powered for efficacy.

D. Background, significance, and rationale (including description of preliminary studies and any results):

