### **Aim 1: Identify and enroll 20 pediatric patients with ASBI and PSH.**

**Methods:** Parent(s)/legal guardians, 18 years or older, will be approached for informed consent if their child has ASBI and is exhibiting clinical signs and symptoms of PSH. Once consented, the CFS scoring tool (Table 1a,) will be used to evaluate patients felt to be exhibiting symptoms of PSH to identify eligible ASBI patients. Patients with CFS score > 6 will be eligible for enrollment in the study.

Families of patients who do not meet the CFS score criteria > 6 will be told their child did not meet scoring criteria of study and will be considered consented but not enrolled in study.

Study Enrollment is defined as meeting CFS criteria of > 6 after consent. If CFS scores are already being collected for subject prior to subject consent as a standard of care, we can use already available CFS scores from medical record. The PENFS device will be placed over the external ear by study investigator or one of trained nurses (RNs) from the Pediatric Translational Research Unit (P-TRU) within 24 hours of meeting CFS > 6 score criteria..

There are 380-400 PICU admissions/year that are seen by ICU Neurology. Using a conservative estimate of 8-10% incidence of PSH, we expect to have 35-40 patients with PSH. At a conservative 60% enrollment rate, we expect to be able to successfully enroll 20 patients in this pilot study. Previous studies using the device has shown it to be well-tolerated with minimal side effects (25,26). In a large, randomized sham-controlled trial Kovacic et al showed a very low rate of discontinuation of the device due to side effects. We hypothesize that the dropout rate will be ≤ 10%. Tolerability of the device will be assessed by subjective assessments of device tolerance by the bedside nurse, the CFS score (increasing score after device placement would suggest worsening PSH symptoms) and skin integrity (bedside nurses will perform routine skin evaluation and care while the device is in place.). To evaluate safety, we will monitor for serious adverse effects such as cardiac dysrhythmia (EKG monitoring), and new-onset seizures.

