### **Aim 2b: Evaluate the effectiveness of the device in reducing PSH symptoms using the change in CFS score**

**Methods:** We will analyze the within-patient change in the modified CFS score with use of the device (before and after device placement and trend in score over time). No maintenance medications will be allowed

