## Protocol Summary/Submission Application

during the initial 12 hours of use of the device; however, rescue medications will be allowed during this period. Maintenance medications would be allowed after 12 hours of device use. We will also compare the trend in scores while using the device to the trend once the device is discontinued after 120 hours of use as we will be following the trend in the CFS scores every 12 hours for an additional 72 hours after removal of the device. This will be impactful as the patient will be his/her own control. However, we recognize that this could be confounded by the initiation of maintenance medications.

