**Table 3: Data collection plan**

	-24 to -12 h	-12 to 0h	Device place ment 0 h		6h	12h	24h	24- 48h	48- 72h	72- 96h	96- 120h	120- 144h	144- 168h	168- 192h
Consent	x													
CFS score		x	x			x	X 12 hourly	x 12 hrly						
Pupillometry		x	x		x	x								
HRV using EKG		x	x		x	x								
Maintenance meds 		x				x	x	x	x	x	x	x	x	x
Rescue Meds 		x				x	x	x	x	x	x	x	x	X
Adverse Events						x	x	x	x	x	x	x	x	X

 No additional new Maintenance Medications are allowed for the first 12 hours after device placement. Patients may remain on Maintenance Medications they are already taking. Additional Maintenance Medication are allowed after the first 12 hours of device placement.

 Patients may continue Rescue Medications during the first 12 hours of device placement.

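### Before/after contrasts in Aims 2b and 3a are shielded from maintenance drugs started just after device placement, but not from drugs started or changed shortly before it

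*Combined protocol and SAP*

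**What the plan says.** The medication rule is in part E, in the section on permitted drugs, and reads: "No additional maintenance medications (propranolol, bromocriptine, dantrolene, gabapentin, baclofen) will be allowed to be initiated for the first 12 hours after initiation of PENFS". Rescue drugs and maintenance drugs already in place may continue, and further maintenance drugs may be added after 12 hours. The same paragraph adds: "Initiation of maintenance medications before placement of PENFS will not be a contraindication to enrollment". Footnote 1 of Table 3 agrees: "Patients may remain on Maintenance Medications they are already taking". The Aim 1 methods allow placement "within 24 hours of meeting CFS > 6 score criteria".

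The Aim 2b methods put the 12-hour rule differently: "No maintenance medications will be allowed" during that period. Aim 2b has two contrasts. One is the within-child change in CFS from before to after placement. The other is described so: "We will also compare the trend in scores while using the device to the trend once the device is discontinued after 120 hours of use". The paragraph closes: "However, we recognize that this could be confounded by the initiation of maintenance medications".

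Aim 3a compares heart rate variability and pupillometry between the 12 hours before and the 12 hours after placement. Its hypothesis is that these measures "will be different after PENFS device placement compared to before, reflecting an increase in parasympathetic tone".

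Table 3 schedules maintenance and rescue drugs in the -12 to 0 h column and from 12 h onward.

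**The concern.** The 12-hour bar makes sense only if a newly started maintenance drug could distort the early contrast. A drug started two hours before placement distorts it in much the same way: it has little time to act in the baseline window and much more in the window after placement. That case is left open.

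It is also a plausible case. Children enter at moderate severity or worse, and the benefits section says symptoms are worst early, when several drugs are needed. The background section lists sympatholytics among the usual treatments for PSH, so a drug effect on autonomic measures could be read in Aim 3a as a device effect.

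At stake is how the before/after changes are interpreted. For recent starts the bias probably favours the device. For dose changes the direction depends on whether the dose went up or down, and the documents do not say.

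**Working it through.** **1. What the rule covers.**

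| Period | New maintenance drug | Dose change to an existing drug |
|---|---|---|
| Qualifying score to placement (up to 24 h) | not barred | not addressed |
| 0 to +12 h | barred | not addressed |
| After +12 h | allowed | not addressed |

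The baseline for both contrasts is the 12 hours before placement, so it lies inside the unrestricted period.

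**2. Whether any analysis picks this up.**
- Mixed models for change over time (data analysis overview): no medication term is named.
- Hypothesis 3a: a Wilcoxon rank sum test with no adjustment stated. The EKG segments are standardised for rest and temperature only.
- Hypotheses 2a and 2b: a Spearman correlation of score with number of doses. This describes an association and does not adjust the before/after change.
- Hypothesis 3b: a classification tree, used for the comparison with historical patients.
- The sensitivity analysis in the overview belongs to the missing-data paragraph.

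The -12 to 0 h medication data are therefore scheduled but unused here. Start times, dose-change times and the -24 to -12 h window are not listed.

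**3. Possible size of the early bias.** The documents give no frequency of recent starts, no half-lives and no drug effect on CFS, so there is no plan figure to reproduce and every input below is an assumption. Take exposure at time t, for a drug started at time s with half-life h, as 1 - 0.5^((t - s)/h), and zero before s. Average it over each window, in percent of steady state:

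| Start | Half-life | -12 to 0 h | 0 to 12 h | Difference |
|---|---|---|---|---|
| -2 h | 3 h | 3.3 | 78.7 | 75.4 |
| -2 h | 6 h | 1.8 | 57.1 | 55.3 |
| -2 h | 12 h | 0.9 | 35.7 | 34.8 |
| -6 h | 3 h | 22.9 | 91.5 | 68.6 |
| -6 h | 6 h | 13.9 | 72.9 | 59.0 |
| -6 h | 12 h | 7.7 | 49.0 | 41.2 |
| -20 h | 3 h | 94.7 | 99.7 | 5.0 |
| -20 h | 6 h | 78.5 | 94.6 | 16.1 |
| -20 h | 12 h | 54.6 | 77.3 | 22.7 |

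(Differences are taken before rounding.) Assume the full drug effect is a fall of 1 to 3 CFS points, proportional to exposure. Then

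shift in mean CFS change = (share with a recent start) x (full effect) x (difference / 100).

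- 2 of 20 children: from 0.10 x 1 x 0.050 = 0.005 to 0.10 x 3 x 0.754 = 0.23 points.
- 5 of 20: from 0.25 x 1 x 0.050 = 0.012 to 0.25 x 3 x 0.754 = 0.57 points.
- 10 of 20: from 0.50 x 1 x 0.050 = 0.025 to 0.50 x 3 x 0.754 = 1.13 points.
- No child: 0.

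The 1.13 needs ten children all starting at -2 h, a 3 h half-life and a 3-point effect.

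**4. The on- versus off-device trend.** The same model gives average exposure in the ten 12-hour windows on device and the six after removal. Straight lines through these have slopes of 0.04 to 10.9 percentage points of steady state per day on device, and at most 0.02 per day off device. The steepest case is a start at -2 h with a 12 h half-life. With a 3-point effect that is 3 x 0.109 = 0.33 CFS points per day of apparent improvement in an affected child while the device is worn, and practically none afterwards. Improvement on device followed by a plateau looks like a device benefit.

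**5. Precision of a drug-stable subgroup.** The 95% CI half-width for a mean change, in SD units, is t(0.975, n - 1)/sqrt(n):
- n = 20: 2.093/4.472 = 0.47
- n = 10: 2.262/3.162 = 0.72
- n = 5: 2.776/2.236 = 1.24

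**The case against.** The plan does not ignore medication. The 12-hour bar is a design control for this very contrast. Table 3 schedules drugs before placement, the data collection section also gathers sedative, pain and other neurotropic drugs, and a practice guideline is meant to keep treatment uniform. Aim 2b concedes confounding by maintenance drugs. The protocol says the pilot is not powered for efficacy and explains why there is no sham arm. All of this stands. It narrows the point to recent pre-placement starts and dose changes, and it makes the point minor.

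It does not remove the point. The Aim 2b caveat follows the on/off comparison, so it reads mainly as a remark on drugs added after 12 hours. It names no adjustment or sensitivity analysis, and Aim 3a has no counterpart.

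Three further limits are fair:
- The sentence on starts before placement concerns eligibility. Starts between enrollment and placement are not expressly permitted; they are simply not barred.
- Drug timing is absent from the listed data, but a summary schedule is not a case report form. A reader might infer that times are not collected; the documents show only that they are not listed.
- The exposure model assumes smooth accumulation and an effect proportional to exposure. It shows direction and a range, and is not an estimate.

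The clash between the two statements of the 12-hour rule is best read as loose shorthand in Aim 2b.

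**Conclusion.** The point holds as a minor one. The early before/after contrasts are protected from maintenance drugs started in the 12 hours after placement, but not from those started or changed shortly before, and no planned analysis or caveat fills that gap for Aim 3a. For recent starts the bias probably favours the device. Its size cannot be learned from the documents and may be zero. The range of 0 to 1.13 CFS points rests wholly on assumed start times, half-lives, effects and frequencies.

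Stronger readings are tempting and are not supported:
- A reader might infer that the on/off comparison is a safeguard because exposure is level around removal. That contrast is of trends, and the early rise on device can tilt it towards the device.
- A reader might infer that recent drug starts would disable the stopping rule by masking a worse CFS. That would need a true worsening and a drug effect large enough to hide it in the same children, and the documents inform neither. The stopping rule also uses comfort scores, dysrhythmia and seizures.
- A reader might infer that the feasibility results are compromised. Early-termination and scoring-completeness rates do not depend on this contrast.

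**What to change.** Leave clinical care, eligibility and the stopping rules as they are.

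1. From the medication record, capture start and dose-change times of maintenance drugs from -24 h to +12 h.
2. Flag a child as drug-stable if there was no maintenance start or dose change from -24 h to 0 h. The flag uses pre-placement data only.
3. Report before/after changes in CFS, heart rate variability and pupillometry for all children and for drug-stable children, with confidence intervals, as a descriptive sensitivity analysis without a test between groups. List rescue use and maintenance dose changes in 0-12 h alongside, without excluding anyone on that basis.
4. Extend the Aim 2b caveat to Aim 3a, to recent pre-placement starts and dose changes, and to the on/off trend.
5. As an editorial matter, reword the Aim 2b rule so that it bars only new maintenance drugs, matching the medication section and Table 3.

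The cost is low: a chart extraction (assuming the inpatient record holds the times), one derived variable, one extra table and two wording changes. The drug-stable group may be small, with the half-widths shown above, so its result can inform but not settle the question. Children treated recently may also differ in severity. Regression to the mean after selection on CFS above 6, and natural improvement, remain whatever is done here.

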### **Aim 3b: Evaluate feasibility of measuring PENFS effectiveness in treating PSH by a decrease in medication use**

**Methods:** The maintenance medications and the number of doses and type of rescue medications administered will be collected for every 24 hours (0-24h, 25-48h, 49-72h, 73-96h, 97-120h, 121-144h, 145-168h, 169- 192h) for the enrolled patients. These will be compared to a historical cohort of PSH patients. The historical cohort will consist of PSH patients (2-17 years old) identified using the ICU Neurology administrative dataset from January 2018 – August 2021. This dataset will be used to identify ASBI patients who likely developed PSH. Eligible patients with PSH will be identified and relevant data collected by individual chart review. During this period all the PSH patients were followed by ICU Neurology thus ensuring a uniform approach to their treatment. We have also developed a practice guideline for treatment of PSH that will ensure uniform treatment of these patients during the study period. Similar to Aim 2a, we will examine the need for additional maintenance medications or change in frequency of rescue medications with discontinuation of the device. We hypothesize that, with discontinuation of the device, the patients may experience worse PSH symptoms as demonstrated by increasing CFS score and need for additional maintenance and/or rescue medications.

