## Protocol Summary/Submission Application

*Hypothesis 1:* The number approached and consented will be tracked. Reactions/ adverse events will be summarized and reasons for early termination, if any, evaluated.

*Hypothesis 2a, 2b:* The scoring tool will be adapted for the appropriate age range of the patient (Table 2). We aim for at least 80% scoring ( $\geq 8/10$  scheduled scoring per protocol while the device is worn). The association of the score and the number of doses of maintenance and rescue medications will be summarized with a spearman correlation and exact 95% Confidence intervals (CI).

*Hypothesis 3a:* HRV and Pupillometry measures will be tracked over time with any loss of data recorded with reasons. Wilcoxon Rank Sum test will be used to compare the mean  $\pm$ SD for the parameters for the 12-hour periods before and after device placement.

*Hypothesis 3b:* The number of doses of maintenance and rescue medications for control of PSH symptoms will be compared to historic data using a t-test or non-parametric Mann Whitney. Further a classification tree will be used to evaluate the effect of demographics, clinical history and use of PENFS.

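### The 12-hour bar on new maintenance drugs binds only device children, so the Aim 3b historical comparison carries a bias unrelated to PENFS, and mismatched time origins leave its net direction uncertain

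*Combined protocol and SAP*

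**What the plan says.** Section E, under the heading on medication during study treatment, states the rule: "No additional maintenance medications (propranolol, bromocriptine, dantrolene, gabapentin, baclofen) will be allowed to be initiated for the first 12 hours after initiation of PENFS". It is repeated a few lines later ("once enrolled, no new maintenance medications would be allowed for the initial 12 hours after device placement") and in footnote 1 to Table 3. After that, "Additional maintenance medications could be instituted beyond the initial 12-hour period if PSH symptoms are not adequately controlled". Drugs already running may continue: "Initiation of maintenance medications before placement of PENFS will not be a contraindication to enrollment". The Aim 2b methods word the bar more broadly, without limiting it to new drugs. I use the narrower form, which the medication section and Table 3 share; the two wordings should be reconciled.

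The Aim 3b hypothesis in Section C is that "PENFS device use will result in lesser number and/or doses of maintenance and rescue medications for control of PSH symptoms". The Aim 3b methods say "The maintenance medications and the number of doses and type of rescue medications administered will be collected for every 24 hours", with 0-24 h as the first block, and set this against children "identified using the ICU Neurology administrative dataset from January 2018 – August 2021". The analysis overview, Hypothesis 3b, says "The number of doses of maintenance and rescue medications for control of PSH symptoms will be compared to historic data", using a t-test or Mann-Whitney test. Section C adds that the comparison is to support the power calculation for a larger efficacy trial.

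The time origins differ. Under Data collection & Management, device children are counted from placement and historical children from meeting CFS > 6. The Aim 1 methods allow placement up to 24 h after CFS > 6.

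**The concern.** For half of the first block, new maintenance starts in device children are fixed at zero by the protocol. No such bar is described for the historical children. A difference in starts over those 12 h therefore reflects the rule and says nothing about the device. Because a drug not started is also not dosed, the rule reaches the planned outcome, number of doses. It may also move symptom control onto rescue drugs, which would bias the rescue comparison the other way.

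The Aim 3b methods, the data collection section and Hypothesis 3b neither separate nor adjust for the restricted window. The one caution about maintenance drugs, in the Aim 2b methods, concerns the within-patient CFS trend. The practice guideline cited under Aim 3b is said to ensure uniform treatment during the study period and does not put the earlier cohort under the bar.

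What is at stake is the estimate handed to the next trial: part of any difference would come from a rule, and part from counting the two cohorts from different moments.

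**Working it through.** The plan has no figure to reproduce. The 20 patients are a convenience sample, and no start rate, SD, alpha or historical sample size is given. The check asks what an inert device would show.

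**From the documents:** no new starts in 0-12 h after placement; starts allowed from 12 h; drugs begun earlier continue; first block 0-24 h; placement 0 to 24 h after CFS > 6; historical clock from CFS > 6.

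**Assumed:** probability p of starting a maintenance drug in any 12 h (constant rate); one drug, dosed every 6 h; placement delay either nil or uniform over 0-24 h. After 12 h there is either full catch-up (every barred start happens at 12 h) or none (the start process begins afresh at 12 h).

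**Starts, no delay, p = 0.3.**
- 0-12 h: 0% device, 30% historical.
- 0-24 h: historical 1 - 0.7² = 51%; device 30% (no catch-up) to 51% (full).

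**Doses in 0-24 h, no delay, p = 0.3.** Expected doses are the sum of the probabilities of having started at least 0, 6, 12 and 18 h before the block ends.
- Historical: (1 - 0.7²) + (1 - 0.7^1.5) + (1 - 0.7) + (1 - 0.7^0.5) = 0.510 + 0.414 + 0.300 + 0.163 = 1.39.
- Device, no catch-up: 0.300 + 0.163 = 0.46.
- Device, full catch-up: 0.3 × 2 + 0.7 × 0.463 = 0.92.

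**Doses in 0-24 h, delay uniform over 0-24 h, p = 0.3.** The hourly rate is -ln(0.7)/12 = 0.0297. The share not yet started at placement is (1 - 0.7²)/(24 × 0.0297) = 0.715, so 0.285 arrive on a drug and receive 4 doses.
- Device: 4 × 0.285 + 0.715 × 0.463 = 1.47 (no catch-up); 4 × 0.285 + 0.715 × 0.924 = 1.80 (full).
- Historical, clock from CFS > 6 as planned: 1.39.
- Historical, clock started after the same delay: 4 × 0.285 + 0.715 × 1.388 = 2.13.

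The same formulas at other values of p give mean 0-24 h maintenance doses per child (device ranges run from no to full catch-up):

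| p | Historical, from CFS > 6 | Device, no delay | Device, 0-24 h delay | Historical, same delay |
|---|---|---|---|---|
| 0.2 | 0.95 | 0.31-0.64 | 1.02-1.29 | 1.54 |
| 0.3 | 1.39 | 0.46-0.92 | 1.47-1.80 | 2.13 |
| 0.5 | 2.19 | 0.79-1.40 | 2.27-2.59 | 3.02 |

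On a common clock (no delay, or the same delay in both cohorts) the inert device always shows fewer doses. On the planned clocks with a 0-24 h delay it shows more.

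**Comparing from 12 h, p = 0.3, doses in 12-24 h.**
- No delay: historical 0.3 × 2 + 0.7 × 0.463 = 0.92; device 0.46 to 0.92.
- Same delay in both: historical 2 × 0.285 + 0.715 × 0.924 = 1.23; device 2 × 0.285 + 0.715 × 0.463 = 0.90, up to 1.23.
- The gap vanishes under full catch-up. Without catch-up it halves: from 0.92 to 0.46 with no delay, and from 0.66 to 0.33 with delay.

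**New starts counted from 12 h, no delay, p = 0.3.** Historical 0.7 × 0.3 = 21%; device 30% to 51%. This count is biased against the device.

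**The case against.** A reader might infer that the design guarantees fewer maintenance drugs with PENFS. The documents do not support that. The planned test is on number of doses, not on starts. Starts over 0-24 h are equal (51% in both cohorts at p = 0.3) if every barred start occurs at 12 h and placement is immediate. For doses, the later device clock and the drugs carried in from before placement can reverse the direction. A reader might also infer that dropping the first 12 h and counting starts afterwards would cure the problem. It would not, because deferred starts pile up just after 12 h.

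The other objections are fair in part. The start rate and its time course are assumed, so no figure here estimates the actual bias. The bar covers 12 of 192 recorded hours. Aim 3b is framed as feasibility, and the protocol says the pilot is not powered for efficacy. Nowhere does it say that maintenance and rescue doses will be summed, and Table 3 lists them in separate rows; reporting them separately is therefore a clarification.

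What stands is that the rule binds one cohort only, falls inside the compared outcome, and is not addressed under Aim 3b. Pilot status does not dispose of this, because the comparison is meant to inform the next sample size.

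**Conclusion.** The concern holds in a limited form. New maintenance starts in 0-12 h are zero by rule in device children, and a difference there is not evidence about PENFS. This matters only if some historical children started a maintenance drug in that window, which the documents do not report. On a common clock, 0-24 h maintenance doses are biased downward with an inert device: at p = 0.3, 0.46-0.92 against 1.39 with no delay, or 1.47-1.80 against 2.13 with a 0-24 h delay in both cohorts. Rescue doses may be biased upward, by an amount that cannot be stated. As the plan is written, the net direction for 0-24 h doses is uncertain because the clocks differ. All magnitudes rest on the assumed start rate, six-hourly dosing, delay and catch-up.

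**What to change.** Change only the analysis text in the Aim 3b methods, Data collection & Management and Hypothesis 3b.

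1. Put both cohorts on a comparable clock. For example, record the time of CFS > 6 in device children, and start each historical child's clock at a delay after CFS > 6 matched to the delays seen in device children.
2. Split the first block into 0-12 h and 12-24 h; Table 3 already has a 12 h column for both drug rows. Report 0-12 h descriptively. Base the maintenance comparison on doses given and drugs in use from 12 h onward, not on new starts counted from 12 h.
3. Report maintenance and rescue doses separately.
4. State that a 0-12 h difference in starts is not evidence of a PENFS effect, that some carry-over past 12 h may remain if catch-up is incomplete, and that the estimate passed to the next trial's sample size comes from the post-12 h comparison.

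The cost is one extra time cut in a chart review already planned, the recorded time of CFS > 6 in device children, and slightly fewer doses in the comparison. The medication rule itself is unchanged.
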